Experimental Approach to the Problem

Research Design

Twenty-four to Thirty healthy, resistance-trained men (n=12-15) and women (n=12-15) between the ages of 18 and 35 will be recruited for this randomized, cross-over investigation. In order to be considered resistance trained, participants will need to have been engaged in resistance trained for ≥ 1 year prior to study enrollment and must be able to leg press at least 2x their bodyweight. Participants must also be free of any physical limitations, metabolic or cardiovascular disorders, and musculoskeletal injuries. Females will be excluded if they are not eumenorrheic and/or report the use of hormone-based contraceptives (e.g. oral contraceptive pill) within the previous 3 months. For female participants, all experimental sessions will take place within the same phase of their menstrual cycle. Furthermore, all participants will be asked not take any other nutritional supplements, performance enhancing drugs, and non-steroidal anti-inflammatory drugs (NSAIDs) throughout the duration of their enrolment in the study. Additionally, participants will be excluded if they have a history of antibiotics or intentionally consumed probiotics in the two months prior to enrollment in the study. If a participant has recently consumed probiotics, an 8-week washout period will be required before the participant is enrolled in the study. The study protocol will be approved by the Lipscomb University Institutional Review Board before participant enrollment.

Testing Procedures

Informed Consent & Questionnaires

Following an explanation of all study protocols, benefits, and risks, each participant will provide their written informed consent prior to participation in this study. Furthermore, participants will complete a PARQ2018+, health and activity questionnaire, food frequency questionnaire, and the Gastrointestinal Symptom Rating Scale (GSRS). The GSRS is an instrument of 15 items combined into five symptom groups representing Reflux, Abdominal pain, Indigestion, Diarrhea and Constipation. The GSRS has a seven-point graded Likert-type scale where 1 signifies absence of troublesome symptoms and 7 represents very troublesome symptoms. The reliability and validity of the GSRS has been previously established (3). The food frequency questionnaire will be used as an additional assessment tool for account for macronutrient and fiber intake when making gut composition comparisons.

Anthropometric & Body Composition Assessment

Prior to all body composition and strength measures, height (± 0.1 cm) and body mass (± 0.1 kg) will be measured for each participant using a Health-o-meter scale (Model 500 KL, Pelstar, Alsip, IL, USA) with the participants standing barefoot, with feet together, in their regular exercise attire.

Total body water (TBW) will be determined using multi-frequency bioelectrical impedance analysis (BIA) using the InBody® 570 Body Composition Analyzer device (Biospace, Inc., Seoul, Korea). Body composition from BIA is obtained from the measures of resistance and reactance when an electrical current travels throughout the body. Prior to each assessment the participants' hands and feet will be thoroughly cleaned with InBody® provided tissues. Age, height, and sex will be manually entered, while a scale positioned within the device assessed body mass. The participant will be then instructed from the software to stand fully erect on the measurement electrodes situated on the platform and to hold hand electrodes, with arms extended, without touching the sides of their body. Participants will be asked to

refrain from moving or talking until the assessment will be completed. It has previously been shown that BIA is a valid measurement tool for determining TBW when compared to a deuterium oxide technique [30].

Body mass, non-bone fat-free mass (FFM), and body fat percentage will be determined using whole body–dual energy x-ray absorptiometry (DXA) scans (ProdigyTM; Lunar Corporation, Madison, WI). Total body estimates of percent fat and non-bone FFM (± 0.1 kg) will be determined using company's recommended procedures and supplied algorithms. Daily calibrations of Quality assurance will be completed prior to all DXA scans using the manufacturer supplied calibration block. All DXA assessments will be completed using standardized subject positioning procedures by a single certified radiological technician.

4-Compartment Model (4C)

Percent body fat will be estimated using a criterion 4C model. We will utilize DXA derived body volume and BMC, while TBW from BIA will be used. This has been previously reported as a valid and reliable method of estimating percent body fat, fat mass, and lean mass (7).

1-Repetition Maximum (1RM) Testing

During the initial visit to the lab, participants will establish their 1-repetition maximal strength (1RM) on the leg press and leg extension exercises. Each participant will complete a standardized warm-up before the 1RM strength session involving 5 minutes of cycling on a cycle ergometer against low resistance, 10 body-weight squats, 10 body weight walking lunges, 10 dynamic walking hamstring stretches, and 10 dynamic walking quadriceps stretches. The 1RM tests will be performed using methods previously described for the leg press and leg extension exercises. Two warm-up sets utilizing a resistance of approximately 40-60% and 60-80% of their estimated maximum for the exercise will be performed. For both exercises, 3-4 subsequent, maximal trials will be completed to determine the 1RM. A 3-5 min rest period will be provided between each trial. Trials which do not meet the range of motion standards for each exercise or where correct technique is not used will be discarded. Foot positioning on leg press sled as well as equipment placement (back, knee, and leg positions) for leg extension will be measured, recorded, and replicated for each participant on subsequent visits. Additionally, any notable attire (such as lifting shoes), which may influence a participant's performance, will be recorded and replicated for each subsequent visit.

Visit 2-3

Study Controls

Following baseline measurements, participants will report to the lab on two additional occasions to complete each experimental condition. On the morning of each visit, participants will be asked to report to the Human Performance Lab (HPL) fasted for 12 hours and asked to refrained from all forms of moderate to vigorous leg exercise over the previous 72 hours. They will also be requested to report after obtaining at least 8-h of sleep and not to have consumed alcohol, nicotine, or any other drug for the previous 36 hours while abstaining from caffeine for the previous 12 hours. To promote hydration, participants will be asked to consume ~500ml of water the night before reporting to the lab, and the morning of each exercise treatment.

Dietary Logs

Participants will be coached to maintain their usual dietary intake in the days preceding the acute resistance exercise trials. Throughout the 24 hours before first experimental trial, each participant will additionally be instructed to record everything they consume in a precise manner. To achieve this, each participant will meet with a registered dietitian for a brief education session to aid in accurate content, quantity, and timing of food in their logs. In subsequent trials, participants will be provided their first dietary log and asked to replicate the content, quantity, and timing of their daily diet during the 24 hours prior to the experimental trial in addition to recording everything they consume. Dietary recalls will be analyzed with the nutrition database, Nutritionix (Syndigo LLC, WA, US).

Stool Collection, Handling and Storage

Participants will be provided with a stool sample collection system during their first visit to the lab and instructed to collect a stool sample in the 24-48 hours prior to reporting for their second visit to the lab to complete the first study condition. Upon arrival to the lab, participants will provide the stool sample and investigators will subsequently aliquot and store samples at -80°C.

Resistance Exercise Protocol

Experimental trials will be completed in a balanced, randomized order with each trial being separated by a minimum of one week to warrant adequate recovery. An overview of the acute resistance exercise protocols is presented in Figure 1. All experimental trials will also be performed within a 2-hour window to avoid diurnal variations. Ample hydration status will be verified (USG ≤ 1.020 defined as euhydration) via urine samples collected upon arrival to the HPL and analyzed for specific gravity (USG) by refractometry. During the exercise experimental trial, participants will perform the same standardized warm-up routine described earlier for 1RM testing, followed by either a resistance exercise protocol, consisting of the squat, seated shoulder press, deadlift, bent-over row, and leg press exercises. The exercise protocol will utilize a load of 70% 1-RM for 4 sets of 10 repetitions and a 90-second rest period length between sets and exercises. The control session will consist of participants completing assessments but will rest seated for 40 minutes instead of exercising. Treatment order (control or exercise) will be randomized using a random number generator. A similar exercise protocol has been demonstrated to significantly elevate I-FABP, a marker of gut permeability (25). During each protocol, if the participant is unable to complete the desired number of repetitions, spotters will provide assistance until the subject completes the remaining repetitions. Immediately upon completion of the acute resistance exercise bout, participants will complete IP assessments.

[figure not shown]

Figure 1. Acute Resistance Exercise Protocol Overview. PRE = Pre-exercise; IP = Immediately-post exercise. RE = Resistance Exercise; GI = Gastrointestinal; 1RM = 1-Repetition Maximum

Acute GI Distress Questionnaires

Before and after the acute resistance exercise protocols (PRE, IP, 60min), participants will complete a questionnaire to assess GI symptoms adapted from a previous study (4). The questionnaire is organized into three sections, each including four to seven questions. Section 1 addresses upper abdominal issues (reflux, heartburn, bloating, cramps, vomiting, nausea); Section 2, lower abdominal issues (intestinal cramps, flatulence, urge to defecate, left abdominal pain, right abdominal pain, loose stool, diarrhea); and Section 3, systemic issues (dizziness, headache, muscle cramp, urge to urinate). Each participant will complete the 17 items on a 10-point scale ranging from 0, no problem at all, to 9, the worst it has ever been.

Blood Collection, Handling and Storage

Blood samples during the experimental trials (PRE, IP, 15min, 30min, 60min) will be drawn from a 20g Teflon™ cannula placed in an antecubital vein, which will remain patent via an isotonic saline flush. Blood samples will be obtained from the cannula with a plastic syringe prior to exercise (PRE), immediately-post (IP), 15-, 30-, and 60min post-exercise. Blood samples will be deposited into untreated (for serum collection), as well as EDTA- and heparin-treated (for plasma collection) BD Vacutainer® tubes. Untreated tubes will clot for 30 minutes prior to centrifugation, while treated tubes will be centrifuged immediately for 15 min at 1500 x g at 4°C. The resulting serum and plasma will be aliquoted and stored at -80°C until analysis. Samples will be thawed only once for biochemical analysis.

Assessment of intestinal damage, permeability, and inflammation

I-FABP concentrations from EDTA plasma will be measured using an ELISA (RayBioTech Inc., Norcross, GA) according to the manufacturer's instructions. Lactulose/Rhamnose (LR) ratio will be assessed using a previously published protocol (2), with the modification of using L-rhamnose instead of mannitol as the monosaccharide probe (5, 6). Briefly, at baseline, participants will drink a standardized sugar solution containing 5 g lactulose, 2 g rhamnose, 1 g sucrose, and 0.5 g D-xylose in a total of 50

mL water. Saccharide concentrations will then be determined from serum samples at all time-points and the LR ratio will be calculated. Serum will be analyzed for endotoxin concentration using a commercially available kinetic limulus amebocyte lysate (LAL) assay (Lonza; Allendale, NJ). Circulating plasma concentrations of the pro-inflammatory cytokine TNF- α will be assayed via commercially available ELSIA kits (ALPCO, Salem, NH, USA).

For fecal analysis, feces will be thawed, and 100 mg will be added to 4.9 ml of extraction buffer (0.1 M Tris, 0.15 M NaCl, 1.0 M urea, 10 mM CaCl₂ 2H₂O, 0.1 M citric acid, 0.5% BSA, pH 8.0). After 30 minutes shaking, 1 ml of suspension will be centrifuged at 10,000 rpm for 20 minutes at 4°C. Fecal supernatants will be assayed for calprotectin via ELISA (Eagle Biosciences, Nashua, NH) using manufacturer's instructions. A summary of the markers of interest is presented in Table 1.

Table 1. Biochemical Markers of Interest

Marker	~24H Pre	Pre	IP	15min	30min	60min	~24H Post
Blood							
I-FABP	X	X	X	X	X	X	
Endotoxin (LAL)	X	X	X	X	X	X	
Lactulose/Rhamnose Ratio	X	X	X	X	X	X	
Fecal							
Shallow Shotgun Metagenomics	X						
SCFA	X						

I-FABP = Intestinal Fatty-acid Binding Protein, LAL = limulus amebocyte lysate, SCFA = Short-Chain Fatty Acids. 24H Pre= 24hours before exercise, Pre= Pre-exercise, IP = Immediately post-exercise, 24H = 24-hours post-exercise.

Fecal Shallow Shotgun Metagenomics

After collection, 10-20g feces will be separated into sterile collection containers and immediately frozen at -20°C. After thawing, DNA will be extracted from samples using the Qiagen MagAttract PowerSoil DNA KF Kit (formerly MO BIO PowerSoil DNA Kit) optimized for the ThermoFisher KingFisher robot according to manufacturer's instructions. Whole DNA will be prepared for sequencing using the Illumina Nextera Flex DNA library prep kit. Samples will be barcoded and mixed together for sequencing. The mix will then be subjected to paired-end sequencing using Illumina sequencers. Paired reads will be concatenated and processed to remove adaptors, barcodes and low-quality reads as well as contaminant sequences (typically host DNA). Sequences will then be mapped to databases to obtain taxonomic and functional profiles. Sequencing will be performed on the Illumina NextSeq. The number of reads targeted ranges from 0.5 to 3 million.

Fecal Short-Chain Fatty Acid Analysis

After collection, 10-20g feces will be separated into sterile collection containers and immediately frozen at -80°C. After thawing, Short chain fatty acids will be extracted from stool in an aqueous solution, analyzed in a gas chromatograph (GC) coupled with a flame ionization detector (FID), using a Thermo TG-WAXMS A GC Column. The analytes will be quantified against a series of stock standard solutions.

Statistical Analysis

Prior to analysis all data will be assessed to ensure normal distribution, homogeneity of variance and sphericity. Non-normally distributed data will be transformed using the natural log (LN) and if sphericity is violated, a Greenhouse Geisser correction will be applied. General Linear Model (GLM) repeated measures analyses [time x trial x sex] will be used to compare trials (RE, CON) for all variables. Following a significant F ratio, separate one-way repeated-measures ANOVA will be performed to assess the effect of time during each trial, and separate paired-samples t-tests will be used to compare trials at each time point. Separate independent t-tests will also be used to evaluate specific differences between sexes when applicable. An alpha level of $p < 0.05$ will be considered statistically significant for all comparisons. Based on a standard deviation of $511 \text{ pg}\cdot\text{ml}^{-1}$ and $347 \text{ pg}\cdot\text{ml}^{-1}$ for post-exertional I-FABP for males and females, respectively (8) and using a standard alpha (0.05) and beta value (0.8), a sample size of $n= 4$ per group was calculated to have adequate statistical precision to detect a $> 110\%$ increase in I-FABP post-exercise. Such increases in I-FABP after exercise have also been correlated with the magnitude of intestinal permeability (9). Current participant numbers are also in accordance with sufficient statistical precision to detect significant differences in gastrointestinal symptoms (1). From the metagenome sequencing the group comparisons of gut microbiota will be analyzed with non-parametric Wilcoxon matched-pair signed rank test and corrected for multiple comparison with Benjamini-Hochberg procedure. Regarding the taxonomic data, all analyses will be made with Quantitative Insights Into Microbial Ecology (QIIME) open-sourced software from the randomly subsampled Operational Taxonomic Unit (OTU) table with rarefaction level matching the sample with the lowest total OTU count. The bacterial diversity of the samples (α -diversity metrics) and statistically significant differences in the OTU abundances will be computed with QIIME. Any correlations between non-normally distributed gut microbiota and other variables will be determined using Spearman's rank correlation coefficient in SPSS. The GLM in SPSS will be used to determine whether differences in taxa occur due to biological sex or whether they are dependent on age, weight, body fat %, total energy intake, macronutrient composition, or fiber.

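### The 72-hour pre-visit rule covers leg exercise only, so unrecorded upper-body training can add noise to the exercise–control contrast (minor)

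*Protocol*

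**What the plan says.** Under Visit 2-3, Study Controls, participants are "asked to refrained from all forms of moderate to vigorous leg exercise over the previous 72 hours". No other section restricts, records or matches upper-body training before visits 2 and 3.

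Under Resistance Exercise Protocol, the bout is described as "consisting of the squat, seated shoulder press, deadlift, bent-over row, and leg press exercises". The same section says "A similar exercise protocol has been demonstrated to significantly elevate I-FABP, a marker of gut permeability (25"), without giving the size or duration of the rise. The reference list stops at 9, so reference 25 cannot be traced.

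The sections on blood collection and on intestinal damage, permeability and inflammation set out I-FABP, endotoxin, the lactulose/rhamnose ratio and TNF-α. The blood draws run from PRE to 60 minutes after exercise. GI symptoms are collected by questionnaire.

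Participants must have been "engaged in resistance trained for ≥ 1 year prior to study enrollment".

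On order: "Experimental trials will be completed in a balanced, randomized order with each trial being separated by a minimum of one week". Under Dietary Logs, participants in later trials are "asked to replicate the content, quantity, and timing of their daily diet during the 24 hours prior to the experimental trial". That rule covers food intake and has no counterpart for exercise.

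Statistical Analysis states: "General Linear Model (GLM) repeated measures analyses [time x trial x sex] will be used to compare trials (RE, CON) for all variables". After a significant F ratio, paired t-tests compare the trials at each time point, with no stated adjustment for PRE.

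**The concern.** The rule protects the legs, which fits the 1RM tests of leg press and leg extension at the first visit. It fits neither the bout, which includes seated shoulder press and bent-over row, nor endpoints measured in blood and gut.

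The uncontrolled factor is of the same kind as the exposure under test. The participants train habitually, so upper-body work between visits is to be expected. The protocol standardises fasting, sleep, alcohol, caffeine, hydration, time of day, menstrual phase and diet before the visits, but prior exercise only in part.

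Two consequences are possible. If upper-body sessions fall before visits irrespective of condition, they add within-person variability to every exercise–control comparison. If they fall more often before one condition, they shift the contrast. The second is conceivable because, with only two conditions, everyone who has completed visit 2 knows what visit 3 will be. Prior exercise that was not recorded cannot be examined or adjusted for afterwards.

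**Working it through.** The protocol states no figure on this point, so there is nothing to reproduce. It also gives no within-person SD for any marker. The SDs of 511 and 347 pg/ml in the sample size paragraph describe post-exertional I-FABP in males and females. They do not describe the exercise–control difference, so results are given in units of the within-person SD, *s*.

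**Inputs**
- From the protocol: two conditions, balanced random order, 24 to 30 participants, paired comparison of trials.
- Assumed: a prior upper-body session shifts a marker at the visit by *d* × *s*, with *d* from 0 to 1. Such a session precedes a share *p* of visits, with *p* = 0.3 or 0.5. Occurrence is independent between a participant's two visits.

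**Noise.** Without prior training the paired difference has variance 2*s*². Each visit adds *p*(1 − *p*)*d*²*s*², so the two visits add 2*p*(1 − *p*)*d*²*s*². The proportional increase is *p*(1 − *p*)*d*².

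| *d* | *p* = 0.3 | *p* = 0.5 |
|---|---|---|
| 0 | 0 | 0 |
| 0.2 | 0.21 × 0.04 = 0.8% | 0.25 × 0.04 = 1.0% |
| 0.5 | 0.21 × 0.25 = 5.3% | 0.25 × 0.25 = 6.3% |
| 1.0 | 0.21 × 1 = 21% | 0.25 × 1 = 25% |

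The range is thus about 0 to 25%. In the extreme corner, 24 participants would give the precision of 24/1.25 = 19.2. If training follows a fixed weekly habit, occurrence before the two visits is positively correlated and the added variance is smaller.

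**Bias.** Bias equals the shift times the difference between conditions in the share who trained beforehand. It is zero when the shares are equal. Suppose behaviour can differ only at visit 3, once the remaining condition is known, and take 50% before a control visit against 20% before an exercise visit. With balanced order, half of each condition's visits fall at visit 2, where the shares are equal:

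- average difference in share = ½ × 0 + ½ × (0.50 − 0.20) = 0.15
- bias = 0.15 × *d*: 0.15 × 0.5 = 0.075 SD and 0.15 × 1 = 0.15 SD

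If the session raises the marker, this lifts the control level and pulls the contrast towards no effect.

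**Where it enters the analysis.** A shift that is constant from PRE to 60 minutes cancels from the time-by-trial interaction, because that term compares changes over time. It does not cancel from a paired t-test at a single time point. A shift that changes during the session remains in both.

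**The case against.** The strongest reply is that no harm is shown. The documents give neither size nor duration for any effect of an upper-body session on these markers. The statement about I-FABP concerns a bout like the trial's whole-body one, and post-exercise sampling stops at 60 minutes. Visits take place in the morning after a 12-hour fast and at least 8 hours of sleep, so even a session the evening before is well separated from PRE. This stands, and it is why the range for noise must start at zero.

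The gap is also narrower than it may look. The rule bars every form of harder leg exercise, which on a plain reading takes in running, cycling, squats and largely the deadlift. What remains is upper-body work. A reader might treat the upper-body share of the bout as a measure of contamination. The documents do not support that, since the make-up of the bout says nothing about carry-over into a later blood sample.

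A reader might further infer that the contrast is biased towards no effect, by 0.15 to 0.30 SD if the same 50% versus 20% split held at both visits. The documents do not support this either. The rule is the same before both conditions, order is balanced, and the protocol does not say that participants learn their condition before visit 2. Any difference in behaviour at visit 3 is itself conjecture.

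Finally, PRE is sampled in both trials, the interaction removes a stable shift, and the t-tests follow a significant F. A PRE imbalance would be visible. Without a record of prior exercise, however, it could not be explained.

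**Conclusion.** The point holds as a minor weakness of design control. The restriction is narrower than the trial's own contrast needs: it allows unrecorded resistance exercise of the upper body shortly before a test of resistance exercise on systemic markers.

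The expected effect is mainly noise, 0 to 25% added variance, and about 1% or less if the carry-over shift is 0.2 SD or smaller. Bias of 0.075 to 0.15 SD requires a shift of 0.5 to 1 SD together with the assumed difference in behaviour at visit 3. The shift, the frequency of training and the split are all assumptions. The protocol supports the possibility of contamination but not its presence or size.

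**What to change.** Reconcile Study Controls with Resistance Exercise Protocol by deleting the word *leg*, so that the 72-hour restriction covers all moderate-to-vigorous exercise, identically before visits 2 and 3. Add a line for prior exercise to the existing 24-hour log, extended to 72 hours for exercise only, so that departures are known and can be examined in the analysis.

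The cost is one or two missed upper-body sessions per participant before each visit, and one extra log entry. A separate rule to replicate exercise is not needed, because a compliant participant would have only light activity to replicate. Mandatory rescheduling is not needed for this purpose either: women must be tested in the same menstrual phase, so a postponed visit could cost a full cycle.

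### The natural-log rule cannot be computed for acute GI symptom scores of 0; applied literally in a complete-case GLM, it selects the symptom sample on the outcome

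*Protocol*

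**What the plan says.** Three statements in the protocol bear on this point.

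- **Transformation (Statistical Analysis).** "Non-normally distributed data will be transformed using the natural log (LN". The rule is general. It has no offset, no instruction for zeros and no fallback if the transformed data are still not normal.
- **Model (Statistical Analysis).** "General Linear Model (GLM) repeated measures analyses [time x trial x sex] will be used to compare trials (RE, CON) for all variables". Paired t-tests between trials at each time point follow a significant F ratio. The non-parametric methods named in that section (Wilcoxon, Spearman) are for gut microbiota.
- **Scale (Acute GI Distress Questionnaires).** "Each participant will complete the 17 items on a 10-point scale ranging from 0, no problem at all, to 9". On timing: "Before and after the acute resistance exercise protocols (PRE, IP, 60min), participants will complete a questionnaire to assess GI symptoms".

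The comparator is a resting session: "The control session will consist of participants completing assessments but will rest seated for 40 minutes instead of exercising". Symptoms are an intended comparison, because the Statistical Analysis section also says the sample is large enough to detect symptom differences. It cites a published study for this and gives no figure.

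**The concern.** A 0-9 symptom rating in healthy adults who have fasted for 12 hours, with one of the two sessions spent seated, is likely to be skewed with a pile-up at 0. That would trigger the log rule, and the rule has no value to return for a score of 0.

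Two things are at stake. The first is the number of people left in the symptom model. The second, more important, is who they are. Someone who scores 0 before exercise and above 0 afterwards shows the very response the trial is looking for, and that person would be left out. Those who stay have symptoms at every time point in both trials, so the comparison of exercise with rest would be conditioned on the outcome.

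**Working it through.** **Plan's own figure.** There is none to reproduce. The n = 4 per group in the Statistical Analysis section concerns I-FABP, and the statement on symptom precision has no numbers behind it.

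**Inputs from the protocol.** Participants: 24 to 30 (Research Design). Cells per participant: 3 time points x 2 trials = 6. Items: 6 upper abdominal, 7 lower abdominal and 4 systemic, 17 in all, each scored 0 to 9.

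**Step 1: the transformation.** ln(0) is minus infinity, so the cell has no usable value. The Gastrointestinal Symptom Rating Scale runs from 1 to 7, where ln is defined, so it is not affected.

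**Step 2: the model.** A standard repeated-measures GLM needs all six cells. A participant stays only if all six scores are above 0. The follow-up paired t-tests likewise lose every pair that contains a zero.

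**Step 3: the number kept.** The documents give no zero rate, so q, the chance of a zero in a cell, is an assumption, taken as equal across cells. If cells are independent within a person, the fraction kept is (1 - q)^6. If they are fully dependent (a person is zero in all six cells or in none), it is 1 - q.

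| q | (1 - q)^6 | kept of 24 | kept of 30 | 1 - q | kept of 24 | kept of 30 |
|---|---|---|---|---|---|---|
| 0.20 | 0.262 | 6.3 | 7.9 | 0.80 | 19.2 | 24.0 |
| 0.30 | 0.118 | 2.8 | 3.5 | 0.70 | 16.8 | 21.0 |
| 0.50 | 0.016 | 0.4 | 0.5 | 0.50 | 12.0 | 15.0 |

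Ratings from one person are expected to be positively correlated, so the truth should lie between these ends. As an illustration, take a beta-binomial model with an assumed intraclass correlation of 0.5. Its parameters then sum to 1, and the fraction kept is the product over i = 0 to 5 of (1 - q + i)/(1 + i). This gives 0.592, 0.442 and 0.226, or about 14, 11 and 5 of 24.

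The fully dependent end is reached only if nobody moves between zero and non-zero. It therefore leaves no room for new symptoms after exercise among people who start at 0.

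**Step 4: does summing items avoid it?** Not necessarily. If each item is non-zero with an assumed probability of 0.05, independently, then the chance that a score is zero is:

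- 6-item upper section: 0.95^6 = 0.74
- 7-item lower section: 0.95^7 = 0.70
- 4-item systemic section: 0.95^4 = 0.81
- 17-item total: 0.95^17 = 0.42

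With a per-item probability of 0.10, the 17-item total is zero with probability 0.90^17 = 0.17. The choice of score changes the problem a good deal, but zeros remain possible in all of them.

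**Step 5: would an offset do?** ln(0 + 1) = 0, so ln(x + 1) keeps all 24 to 30 participants. All zeros still map to one value, so the pile-up remains and the data are not made normal.

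**The case against.** The best defence is that several links in the chain are inferred. The log applies only if the scores are judged non-normal. The protocol does not say that undefined values become missing or that incomplete cases are dropped. It does not say whether items, section totals or the 17-item total are analysed, and a total that includes flatulence and the urges to defecate and urinate will be zero less often than a single item. A statistical analysis plan that is not shown may deal with zeros. An undefined logarithm is conspicuous in software, the raw scores are untouched, and the stated sample-size calculation rests on I-FABP, not symptoms.

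Most of this stands as a limit on certainty and on weight. It does not remove the point. The protocol is not silent: it states one rule and one model for every variable, and for this scale the rule cannot be computed at 0. An analyst who notices would have to improvise after seeing the data, and the obvious improvisation (an offset) does not cure the distribution.

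A reader might go further and infer that symptom-free participants are certain to be deleted, or that no analysable sample will be left. The documents do not support either. No deletion is stated and no zero rate is given. Retention near zero needs a rate of about 50% together with independent cells within a person; at the same rate, full dependence keeps 12 of 24.

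**Conclusion.** The point holds in conditional form. Followed literally, the log rule fails for any symptom score of 0, and with a complete-case GLM it removes participants according to their outcome. At assumed zero rates of 20%, 30% and 50% the number kept of 24 lies between about 6 and 19, 3 and 17, and 0 and 12 respectively. The width reflects the unknown within-person dependence; the zero rates and the score to be analysed are also unknown.

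The selection does not depend on the exact count: whatever the rate, those dropped are the people with a symptom-free cell. The weight is a should-fix rather than a must-fix. The defect is confined to one symptom questionnaire, it does not touch I-FABP or data collection, and it can be corrected in the text before analysis.

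**What to change.** In the Statistical Analysis section:

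1. Limit the natural-log rule to strictly positive laboratory concentrations.
2. Name the GI symptom score to be analysed, for example the 17-item total (0 to 17 x 9 = 153), with the three section totals (0-54, 0-63 and 0-36) as secondary.
3. Analyse it with a method that keeps zeros. One option is an ordinal mixed model with trial, time and sex. The other is a paired rank test of exercise versus control on change from PRE at IP and 60 min, with stated handling of zero differences (for example Pratt's method, since the usual signed-rank test discards them).
4. If the rank test is chosen, state a multiplicity correction over sections and time points. Three sections x two time points is 6 tests, and adding a sex contrast to each makes 12, with no F test in front of them.

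The change takes a few sentences and no new data. Its costs are that symptoms no longer share the three-way F test used for the other variables, and that the rank test loses some power when many differences are zero. Differencing summed ordinal items also treats them as roughly interval-scaled; the ordinal model avoids differencing, though a total still adds up items.
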